8. STUDY CALENDAR

	Base line ^e	Day 1 to Day 7	Day 8 ^b	Day 9	Day 10	Day 11	Day 12 ^c	Day 13 to Day 30	Month 1 ±2wk	Month 6 ±1mo	Month 12 ±1mo
Informed Consent	x										
GLN		x	x	x	x	x	x	x			
APBI			x	x	x	x	x				
RTOG Acute	x						x		x		
Cosmetic score	x						x		x	x	x
RTOG Chronic									x	x	
CBC	x		x				x		x		
Myoglobin	x		x				x				
Study Lab ^d	x		x				x		x		
Mammogram/Breast Density ^a	x									x	x
Performance Status	x						x		x	x	
A quality of life questionnaire	x						x		x	x	
An open-ended question									x	x	
Adverse event assessment				x			x		x	x	x

- a. A bilateral digital mammogram will be performed in the range ≤ 6 months prior to lumpectomy as per standard treatment to rule out recurrence and measure density.
- b. Day 8 is start of APBI.
- c. Day 12 is end of APBI.
- d. Blood will be drawn for the measurements of non-enzymatic and enzymatic antioxidants, reactive oxygen metabolites, lipid peroxidation, oxidative DNA damage, protein oxidation, myoglobin, complete blood count, NK cell activity, and cytokine production.
- e. A window of 2 weeks will be allowed from Baseline to Day 1. All baseline procedures must be completed prior to subject starting glutamine.

9. RISKS AND TOXICITIES TO BE MONITORED**a. Potential Toxicities, Risks and Precautions**

Procedure	Risks	Measures to Minimize Risks
Complete history and physical exam, including blood chemistries	Identification of previously unknown condition	Qualified health care provider to evaluate potential subject
Collection of blood samples	Pain, bruising at the injection site and rarely infection Discovery of previously unknown conditions Possible breach of confidentiality	Experienced personnel will perform the phlebotomies using approved techniques. Pressure and dressings will be used to minimize pain, bruising and infection. Research records are kept in a locked area accessible only by study personnel.

Procedure	Risks	Measures to Minimize Risks
		Subject study numbers will be used for identification of samples so that confidentiality is ensured.
Glutamate sensitivity	Headache, flushing, sweating, facial pressure or tightness, numbness, tingling or burning in the face, neck or other areas, rapid, fluttering heartbeats, chest pain, nausea, and/or weakness	Qualified health care provider to evaluate potential subject

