10. DATA HANDLING AND RECORD KEEPING

a. Registration Procedures

Subjects will be registered in C3PR, a cancer Biomedical Informatics Grid (caBIG® NCI) application.

b. Methods for Data Collection and Data Collection Tools

Data will be entered into OpenClinica through electronic web-based case report forms (CRFs) which replicate the paper CRFs attached to this protocol. OpenClinica is a secure open source system for electronic data capture and clinical data management. Data will be stored as required per regulations.

c. Confidentiality, Storage and De-Identification of Data

Government agency regulations and directives require that the study investigator retain all study documentation pertaining to the conduct of a clinical trial. Study documents should be kept on file until three years after the completion and final study report of this investigational study.

11. CRITERIA FOR EVALUATION**a. Outcome measures for Specific Aim 1**

i. Primary efficacy outcome:

- Excessive Toxicity, which will be defined as an acute radiation-toxicity score of 2 or higher on either Day 12 (the last day of APBI) or at the one-month follow-up visit. Acute radiation toxicity will be scored as described below using the RTOG Acute toxicity-scoring criteria.

ii. Secondary efficacy outcomes:

- Acute radiation toxicity, which will be scored using the RTOG Acute toxicity-scoring criteria. These range from 0 (no change) to 4 (necrosis). Acute radiation toxicities will be scored on Day 0 (baseline, a week before APBI), Day 12 (the last day of APBI), and at the one-month follow-up visit.

- A score of 2 or higher on the RTOG Acute scale will be considered to be excessive toxicity if it is scored on either Day 12 or at the one-month follow-up visit (see Excessive Toxicity above).

- Chronic radiation toxicity, which will be scored using RTOG LENT/SOMA criteria. These range from Grade 1 (minimal hypersensation) to Grade 4 (refractory). Chronic radiation toxicities will not be scored at baseline, but will be scored during the follow-up visits at 6, and 12 months.

- Breast cosmesis, which will be scored using a subject-and-physician point-scoring system. Breast cosmesis will be scored at Day 0 (baseline), Day 12 (the last day of APBI), and during the 1 month, 6 month, and 12 month follow-up visit.

- Breast density, which will be determined by mammogram at baseline and during the follow-up visits at 6 and 12 months.

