- Performance Status, which will be assessed using questionnaire. Performance status will be assessed on Study Days 0, 12, and during the follow-up visits at 1 and 6 months.

- Quality of life, which will be determined using questionnaire. The quality-of-life questionnaire will be assessed on Study Days 0, 12, and during the follow-up visits at 1 and 6 months.

- An open-ended question (How was your experience with this treatment?), which will be answered by the subject. An open-ended question will be assessed during the follow-up visits at 1 and 6 months.

- Additional subject data to be collected will be BMI, meds, steroids, smoking, alcohol, etc. Stratification using these criteria will be considered but unlikely to be significant in this small pilot trial.

b. Outcome measures for Specific Aim 2

Assays of all outcome measures will be performed on blood samples obtained at the following times from each subject: Day 0 (baseline, the day before GLN/placebo begins), Day 8 (just before APBI commences), Day 10 (the third day of APBI), Day 12 (the last day of APBI), and at the 1-month follow-up visit (the day when GLN/placebo ends).

- Measures of oxidative stress, antioxidant defense and a potential biomarker for GLN effect:
 - Levels of enzymatic antioxidants such as glutathione peroxidase (GPx), glutathione S-transferase (GST), superoxide dismutase (SOD), and catalase (CAT).
 - Levels of non-enzymatic antioxidants, namely, glutathione in both its reduced (GSH) and oxidized (GSSG) form.
 - Reactive oxygen species such as the superoxide anion (O_2^-) and hydrogen peroxide (H_2O_2).
 - Lipid peroxidation products such as malondialdehyde (MDA) and/or 4-hydroxynonenal (4-HNE).
 - DNA-oxidation products such as 8-hydroxy-2'-deoxyguanosine (8-OHdG).
 - Protein-oxidation markers such as the carbonyl derivatives of proline, lysine, arginine and threonine residues.
 - A potential biomarker for GLN effect such as myoglobin.
- Measures of immune response:
 - Complete blood count (CBC)
 - NK-cell activity.
 - Production of cytokines such as interferon-gamma (IFN- γ) and tumor necrosis factor-alpha (TNF- α).

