Data for each secondary-efficacy outcome measure will be summarized by assessment time and study arm, using mean scores and proportions for Likert-scaled data (acute radiation toxicity, chronic radiation toxicity, and performance status), and using means and standard deviations (SDs) for continuous and quasi-continuous data (breast cosmesis, and quality of life). Data will be graphed versus assessment time as stacked barcharts or profile plots depending on the outcome measure. Treatment-arm differences over time will be assessed using longitudinal-analysis methods, namely, (A) logistic and cumulative-logistic regressions with generalized estimating equations for dichotomized and Likert-scaled data, respectively, and (B) repeated-measures ANOVAs for continuous and quasi-continuous data. Post-hoc comparisons between study arms at each time point will employ an alpha=5% significance level despite the multiple testing, in order not to inflate Type II error in this pilot Phase II study.

c. Statistical analysis plan for Specific Aim 2

For each assay endpoint, data will be summarized by study arm and collection timepoint as means and SDs, and graphed versus time as profile plots. Adherence to distributional assumptions will be examined, and data transformations will be applied if warranted. Repeated-measures ANOVA will be used to compare each assay endpoint for study-arm differences over time. Post-hoc comparisons between study arms at each time point will employ an alpha=5% significance level despite the multiple testing, in order not to inflate Type II error in this pilot Phase II study.

d. Missing, Unused and Spurious Data

Missing data will be treated as missing, and will not be imputed. Spurious data will be corrected at the source document. Any data documented as spurious that is unable to be corrected at the source will be treated as missing.

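### The per-visit arm comparisons of cosmesis, quality of life and the Aim 2 assays name no Day 0 covariate, which costs power if baseline correlation is moderate or higher

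*Combined protocol and SAP*

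**What the plan says.** Section 12.b.ii assigns cosmesis and quality of life to its second class of longitudinal method ("B) repeated-measures ANOVAs for continuous and quasi-continuous data"). Section 12.c does the same for the assays: "Repeated-measures ANOVA will be used to compare each assay endpoint for study-arm differences over time". Both sections then state "Post-hoc comparisons between study arms at each time point will employ an alpha=5% significance level despite the multiple testing", and both give the reason: "in order not to inflate Type II error in this pilot Phase II study".

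The baseline values are scheduled:

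- Cosmesis, section 11.a.ii: "Breast cosmesis will be scored at Day 0 (baseline), Day 12 (the last day of APBI"), then at 1, 6 and 12 months.
- Quality of life, section 11.a.ii: "The quality-of-life questionnaire will be assessed on Study Days 0, 12, and during the follow-up visits at 1 and 6 months".
- Assays, section 11.b: a Day 0 sample the day before study product begins, then later draws.

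Note e to the study calendar (section 8) fixes the order: "All baseline procedures must be completed prior to subject starting glutamine". For the assays, section 12.c adds "Adherence to distributional assumptions will be examined, and data transformations will be applied if warranted".

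Section 12 mentions no baseline covariate, change score or constrained-baseline model. The only subject covariates raised are those at the end of section 11.a.ii (BMI, smoking and similar), where stratification is left as a possibility. That does not cover the Day 0 value of the outcome itself.

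**The concern.** The plan tolerates many tests at 5% because it wants to protect power in a small trial. Adjusting each per-visit comparison for the Day 0 value serves the same aim, using data already scheduled and without raising the nominal alpha of any test. Because Day 0 precedes treatment, it is a legitimate covariate.

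If the comparison at a visit uses only that visit's values, stable differences between women stay in the error term. With about 25 per arm that matters: the unadjusted test reaches 80% power only for differences of about 0.81 SD. All of Aim 2, and the cosmesis and quality-of-life parts of Aim 1, rest on analyses of this kind. If the covariate is not named in advance, adding it after the code is broken would look data-driven.

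**Working it through.** **The plan's own figure.** Section 12.a states 91.1% power for the primary outcome (Fisher's exact test, two-sided 10%, 25 per arm, 50% versus 90%). Exact enumeration over two binomial arms of 25 gives 91.14%, so it reproduces. It concerns a binary outcome and does not change here. The plan gives no power figure for the outcomes at issue.

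**Inputs**

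- n = 25 per arm: section 12.a.
- Alpha 5% per visit: sections 12.b.ii and 12.c. Sidedness is not stated; two-sided is assumed.
- Difference d of 0.7 SD or 0.5 SD: assumed.
- Correlation ρ of Day 0 with a later visit, 0.1 to 0.7: assumed.

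**Unadjusted comparison at one visit.** In SD units the variance of the arm difference is 2/n, so the noncentrality is d√(n/2), with 48 df.

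- d = 0.7: 0.7 × √12.5 = 2.475; power 67.9%.
- d = 0.5: 0.5 × √12.5 = 1.768; power 41.0%.

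**Adjusted for Day 0.** The variance is multiplied by (1 − ρ²). Estimating the slope adds an average factor of 1 + 1/(2n − 4) = 1 + 1/46 = 1.0217 and uses one degree of freedom (47 df). The noncentrality becomes d√(n/2) / √[(1 − ρ²) × 1.0217]. At ρ = 0.5 and d = 0.7, the factor is 0.75 × 1.0217 = 0.766, and 2.475/√0.766 = 2.827, giving 79.1%.

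| ρ | 1 − ρ² | With slope cost | Power, 0.7 SD | Power, 0.5 SD | Detectable at 80% power |
|---|---|---|---|---|---|
| Unadjusted | – | – | 67.9% | 41.0% | 0.81 SD |
| 0.1 | 0.99 | 1.012 | 67.4% | 40.6% | 0.81 SD |
| 0.3 | 0.91 | 0.930 | 71.0% | 43.5% | 0.78 SD |
| 0.5 | 0.75 | 0.766 | 79.1% | 50.8% | 0.71 SD |
| 0.7 | 0.51 | 0.521 | 91.9% | 67.0% | 0.58 SD |

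**Break-even.** Setting (1 − ρ²)(1 + 1/46) = 1 gives ρ² = 1/47, so ρ is about 0.15. At ρ = 0 and d = 0.7, adjusted power is 67.0% against 67.9%, a loss of about one point.

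**Why not a change score.** Its variance factor is 2(1 − ρ): 1.40 at ρ = 0.3, 1.00 at 0.5 and 0.60 at 0.7. It is worse than no adjustment below 0.5, and worse than the covariate at each of these values.

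**The case against.** The strongest reply is that the evidence is silence. The plan names a model family and an alpha level; it does not exclude adjustment, and the sentence on 5% tests is about multiplicity. That stands. A reader might infer that the plan has chosen unadjusted comparisons, but the documents support only that no Day 0 covariate is specified.

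Second, the main analysis may already use Day 0. If Day 0 is one level of time in the ANOVA, the arm-by-time test uses it implicitly as change from baseline. This also stands. A reader might infer that the whole longitudinal analysis loses power; the documents do not support that. The loss calculated here belongs to the between-arm comparison at a single visit, which does not use Day 0 in either case.

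Third, the size is assumed. Nothing in the documents shows that any of these outcomes reaches a correlation of 0.5, and one value is unlikely to hold from Day 8 to Month 12 or across all assays. This limits the claim to a range. It does not remove the case, because the trade is uneven: at 0.7 SD, about one point lost at worst, against about 11 gained at 0.5 and 24 at 0.7.

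Fourth, a mixed model can also gain by using the early visits of subjects who later drop out. That gain is not due to Day 0 and should not be credited to it. The figures above compare the same 25 per arm with and without the covariate.

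**Conclusion.** The point holds as an optional improvement in efficiency. Sections 12.b.ii and 12.c leave the Day 0 value out of the specification of the per-visit comparisons, although it is collected before treatment. At 25 per arm, two-sided 5% and an assumed 0.7 SD effect, naming it changes per-visit power from 68% to 67%, 71%, 79% or 92% at assumed correlations of 0.1, 0.3, 0.5 or 0.7. The gain is nil at 0.1, small at 0.3 and material from about 0.5.

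A reader might go further and infer that the planned tests are biased or invalid. They are not: randomisation keeps the unadjusted comparisons unbiased. The primary outcome, its power and the sample size are untouched, and the outcomes concerned are secondary or mechanistic. Confidence in the size is medium, because the correlations and SDs are not in the documents.

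**What to change.** In sections 12.b.ii(B) and 12.c, state that post-baseline values are analysed in a repeated-measures mixed model with arm, visit, arm-by-visit and the Day 0 value. Day 0 should be on the same scale as the outcome, including any transformation, with its slope allowed to differ by visit. Specify small-sample degrees of freedom (for example Kenward-Roger), and say that the per-visit arm differences at 5% are taken from this model. Settle this before unblinding.

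The cost is SAP wording, slightly more modelling, one slope per visit to estimate, and about one power point if the correlation is near zero. Because section 12.d rules out imputation, a subject with no usable Day 0 value leaves that endpoint's model. A constrained-baseline version, which treats Day 0 as an outcome with a common mean across arms, avoids this. No extra visits, subjects or blood draws are needed.

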- Blood will be drawn for the measurements of non-enzymatic and enzymatic antioxidants, reactive oxygen metabolites, lipid peroxidation, oxidative DNA damage, protein oxidation, myoglobin, complete blood count, NK cell activity, and cytokine production. Blood (approximately 45ml) will be collected in Sodium Heparin (green top) tubes and 5 ml blood collected in serum (red top) tubes.
- A quality of life questionnaire will be completed by the subject.
- Performance status will also be determined.
- The subject will have breast skin graded by RTOG acute scoring system.
- A subject and physician point scoring system for breast cosmesis will be completed.
- The next appointment for the subject will be made and subject will be released from the UAMS Radiation Oncology Center.
- Adverse Event assessment

Month 1 Visit:

- The subject will complete GLN/placebo.
- Subject will return any unused GLN/placebo to monitor treatment compliance (measure unconsumed product). This will be used to measure compliance as a percentage of product dose taken. It will also be used to correlate with serum levels of glutamine. Analysis will be performed on intent to treat.
- Glutamine diary will be returned to the study personnel.
- Blood will be drawn for the measurements of non-enzymatic and enzymatic antioxidants, reactive oxygen metabolites, lipid peroxidation, oxidative DNA damage, protein oxidation, complete blood count, NK cell activity, and cytokine production. Blood (approximately 45ml) will be collected in Sodium Heparin (green top) tubes and 5 ml blood collected in serum (red top) tubes.
- A quality of life questionnaire will be completed by the subject.
- Performance status will also be determined.
- The subject will have breast skin graded by RTOG acute scoring system.
- A subject and physician point scoring system for breast cosmesis will be completed.
- An open-ended question for subjects regarding their experience with the study supplement (glutamine/placebo) and radiation treatment will be completed by the subjects.
- Subjects will be examined for recurrence.
- Adverse Event assessment
- The next appointment for the subject will be made and subject will be released from the either the UAMS Breast Surgical Oncology clinic or the UAMS Radiation Oncology Center.

Month 6 Visit:

- A bilateral mammogram will be performed.
- The subject will continue to be grade by per guidelines on RTOG LENT/SOMA Scoring System.

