12. STATISTICAL CONSIDERATIONS

a. Sample Size and Power

Sample-size considerations are motivated by the statistical analysis plan for the primary efficacy outcome (see below), in which a two-sided Fisher's exact test will be used at 10% alpha to compare the glutamine arm to the placebo arm for a statistically significant decrease in the proportion of excessive toxicities. Rubio *et al.*¹⁷ reported the results of a pilot study of oral glutamine supplementation versus placebo in 17 breast-cancer subjects receiving radiation as part of breast-conservation therapy. By the 7th week of their study, all 8 subjects taking placebo (100%), but only 4 of 9 subjects taking glutamine (44%), experienced scores of ≥ 2 on the RTOG Acute toxicity scale. Their results are consistent with excessive-toxicity rates of at least 90% on the placebo arm, but at most only 50% on the glutamine arm. To calculate power, we hypothesize that excessive toxicity rates in our study will be equal to 50% with glutamine versus 90% with placebo. Calculations using PASS 12 software¹⁸ show that a total of 50 study subjects, 25 randomized to the glutamine arm and 25 randomized to the placebo arm, give the two-sided Fisher's exact test 91.1% power at 10% alpha to detect the hypothesized difference in excessive-toxicity rates between the glutamine arm and the placebo arm. This result demonstrates that 25 subjects per study arm (50 subjects total) give this proposed study sufficient

power to achieve the radiation-toxicity-reduction part of its primary objective. To protect against dropouts, a total of 60 subjects will be enrolled and randomized in order to ensure that 50 subjects complete the study.

b. Statistical analysis plan for Specific Aim 1

i. Analysis plan for the primary efficacy outcome

The number of excessive toxicities on each study arm will be reported both as a raw count and as a proportion of the number enrolled per arm. The study-arm difference in excessive-toxicity proportions will be tested for statistical significance using a two-sided Fisher's exact test at an alpha=10% significance level.

ii. Analysis plan for the secondary efficacy outcomes

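### Repeated-measures ANOVA without imputation, in its classical form, drops subjects with any missed visit and assumes sphericity; a mixed model using all visits should replace it in 12.b.ii(B) and 12.c

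*Combined protocol and SAP*

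**What the plan says.** Section 12.b.ii splits the secondary outcomes by data type. Dichotomized and Likert-type outcomes get "logistic and cumulative-logistic regressions with generalized estimating equations for dichotomized and Likert-scaled data". Cosmesis and quality of life get "repeated-measures ANOVAs for continuous and quasi-continuous data". For Aim 2, Section 12.c states: "Repeated-measures ANOVA will be used to compare each assay endpoint for study-arm differences over time". Neither section names an estimation method, a covariance structure, a sphericity correction or an analysis set.

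The missing-data rule in 12.d is "Missing data will be treated as missing, and will not be imputed". Section 12.a allows for dropout: "a total of 60 subjects will be enrolled and randomized in order to ensure that 50 subjects complete the study". Intent to treat appears once, in the Month 1 visit list of Section 7.d, within the item on returned product and compliance: "Analysis will be performed on intent to treat".

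The visit schedules differ by outcome:

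- **Cosmesis** (11.a): Day 0, Day 12 and "during the 1 month, 6 month, and 12 month follow-up visit", so five assessments.
- **Quality of life** (11.a): Day 0, Day 12, Months 1 and 6, so four.
- **Aim 2 assays:** 11.b lists five draws (Days 0, 8, 10, 12 and Month 1). The visit list in 7.d and the calendar in Section 8 have four, with no draw on Day 10.

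**The concern.** Classical repeated-measures ANOVA, whether split-plot or multivariate, needs a complete row for each subject. With imputation ruled out, a woman who misses one cosmesis visit loses her other four from the arm-by-time test. The test then rests on those seen every time. If missing a visit depends on earlier scores, and differently by arm, the arm difference among those women is biased as well as less precise.

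The split-plot F-test also assumes sphericity, that is, equal variance of the difference between every pair of visits. Visits days apart and visits months apart are unlikely to meet this. Without a correction the test rejects too often.

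The choice between a complete-row test and an all-data model changes both the sample and the result. Under 7.b the drug codes go to the statistician for the final analysis, so a choice left open now could be made with assignments known.

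**Working it through.** **The plan's own figures.** The only power figure is for the primary test. Exact enumeration of two binomials (25 per arm, 50% versus 90%) with a two-sided Fisher test at 10% gives 0.9114, which matches the stated 91.1%. The enrolment figure is also consistent: 50/(1 − 1/6) = 60. Neither depends on the ANOVA, and no power is stated for the continuous outcomes.

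**Subjects kept with complete rows.** Inputs: 60 randomised (12.a), and baseline taken as observed, because calendar note e requires it before dosing starts. The documents give no per-visit missing rate, so m = 5% and 10%, independent across later visits, are assumptions. With k assessments, the number kept is 60 × (1 − m)^(k−1).

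| Outcome | k | m = 5% | m = 10% |
|---|---|---|---|
| Cosmesis | 5 | 60 × 0.95⁴ = 48.9 | 60 × 0.90⁴ = 39.4 |
| Quality of life; calendar blood draws | 4 | 60 × 0.95³ = 51.4 | 60 × 0.90³ = 43.7 |
| Myoglobin (calendar row) | 3 | 60 × 0.95² = 54.1 | 60 × 0.90² = 48.6 |

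The share of collected values discarded is 1 − k(1 − m)^(k−1) / [1 + (k−1)(1 − m)]. For cosmesis at 5% this is 1 − 4.07/4.80 = 15%, and at 10% it is 1 − 3.28/4.60 = 29%. For four visits the shares are 11% and 21%.

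**Precision, if per-visit contrasts also come from complete rows.** The detectable difference at two-sided 5% and 80% power is (1.960 + 0.842) × √(2/n) SD, with n per arm. For cosmesis:

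- At 5% missing, all values at one visit give n = 30 × 0.95 = 28.5 and 0.74 SD. Complete rows give n = 30 × 0.95⁴ = 24.4 and 0.80 SD.
- At 10% missing, n = 27 gives 0.76 SD. Complete rows, n = 19.7, give 0.89 SD.

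**Bias.** In one assumed scenario there were four visits, 30 per arm, correlation 0.6 and no true difference. Dropout after the second visit was 17% at random on placebo. On glutamine it was 34% among women scoring below the mean at the second visit. Complete rows gave an arm difference of 0.08 SD at the last visit (simulation standard error 0.017). A mixed model gave −0.02 (0.016).

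**Sphericity.** The uncorrected arm-by-time F-test was simulated with 25 per arm at the plan's visit times, with correlation decaying over time (assumed 0.5 to 0.9 at 30 days). Its size at nominal 5% was 7.0% to 9.2% for cosmesis and 8.4% to 8.8% for the five draws of 11.b. With equal correlation and only unequal variances it was about 5.9%.

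**Reach of the dropout allowance.** The 10 of 60 (16.7%) concerns completing a study that runs to Month 12. Quality of life ends at Month 6 and Aim 2 at Month 1. The allowance therefore bears mainly on cosmesis, partly on quality of life and little on Aim 2.

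**Day 10.** If Day 10 were a required level in a classical ANOVA, no subject following the calendar would have a complete row.

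**The case against.** The strongest reply is that the plan never says incomplete subjects are dropped. Section 12.b.ii presents these as longitudinal methods. The term repeated-measures ANOVA is sometimes used for a mixed-model fit, which keeps incomplete subjects, and a no-imputation rule is compatible with that. This stands: the loss is conditional on the classical form. It does not settle the matter, because nothing in Section 12 points to a mixed model, and the same sentence names a method that can use incomplete subjects only for the other data types.

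Four stronger readings are tempting, and the documents do not support them:

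- **That the plan contradicts its own intent-to-treat rule.** The statement sits in a compliance item and its scope is not defined, so this is a tension.
- **That 17% of subjects are lost from every continuous analysis.** Aim 2 ends at Month 1, so later dropout does not touch it.
- **That 23% to 41% of subjects are lost** (1 − 0.95⁵ and 1 − 0.90⁵). That counts baseline as a visit that can be missed, against calendar note e.
- **That power at one visit falls from 79% to 62%** for a 0.75 SD difference. That sets one-sixth dropout on one side only. With the same dropout on both sides it is 72% versus 62%, and the per-time-point comparisons need not use complete rows at all.

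It is also fair that these are secondary and mechanistic outcomes in a pilot that openly leaves multiplicity unadjusted, and that 12.c promises to examine distributional assumptions. That promise names no sphericity correction, and 12.b.ii makes none.

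**Conclusion.** The concern holds in conditional form. As worded, the plan permits an analysis of cosmesis, quality of life and the Aim 2 assays that keeps only subjects with every visit and assumes sphericity.

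If the classical form is used, the arm-by-time test would keep about 49 to 39 of 60 subjects for cosmesis and about 51 to 44 for the four-visit outcomes. Its size would be about 7% to 9% if uncorrected. The counts rest on an assumed 5% to 10% missing per later visit with baseline observed. The size rests on assumed time-decaying correlation and is nearer 6% when only the variances differ.

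The primary Fisher test and the GEE outcomes are not affected, and the per-time-point comparisons need not be. The change should be made, but it does not threaten the trial's main conclusion.

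**What to change.** In 12.b.ii(B) and 12.c, replace repeated-measures ANOVA with a linear mixed model for repeated measures fitted by REML:

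- every available visit of every randomised subject;
- fixed effects for arm, visit and arm-by-visit;
- unstructured within-subject covariance, which has 5 × 6/2 = 15 parameters at five visits and 4 × 5/2 = 10 at four;
- a simpler fallback stated in advance if the model does not converge, for example heterogeneous Toeplitz;
- small-sample degrees of freedom such as Kenward-Roger;
- per-visit arm contrasts taken from this model.

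This is compatible with the no-imputation rule in 12.d, and it states the analysis set for these outcomes. Section 11.b must also be reconciled with the visit list in 7.d and the calendar in Section 8 on the Day 10 draw, so that the visit levels in the model are defined.

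The cost is about two sentences of wording and slightly more modelling work with standard software. No new data are needed. The model assumes data are missing at random, which is weaker than what a complete-row analysis needs.
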